### 3.7.2 Sample Size Calculation for Mother-Infant Dyads

The sample size for mother-infant dyads was calculated using the two-sample independent t-test. This was based on a previous study and this study's primary outcome (Rao, Udani, & Nanavati, 2006). The two-tailed comparison group was used in the sample size calculation using the formula below. The mean difference in weight gain was 8.41 (Rao et. al., 2006) pre and post-intervention, while 0.8 was the standard deviation. These values were applied in the formula based on the study done by Rao et., al (2006).

$$\text{The formula, } n = \frac{2[Z\alpha/2 + Z\beta]^2 S^2}{(\mu_1 - \mu_2)^2}$$

$$\text{Thus, } Z\alpha/2 = 1.96 \quad Z\beta = 0.842$$

$$\mu_1 - \mu_2 = 0.54 \quad S = 0.8$$

$$\text{The formula, } n = \frac{2[1.96 + 0.84]^2 [0.8]^2}{(0.54)^2}$$

$$n = \frac{2 [ 2.802 ]^2 (0.64)}{0.29}$$

$$n = \frac{2 [ 7.85 ] (0.64)}{0.29}$$

$$n = \frac{10.05}{0.29}$$

Thus,  $n = 34.65 = 35$  subjects for each group.

Additional 30% = 50 subjects for each group.

An additional 30% was added to the estimated sample size to account for possible missing values and non- responses. The final sample size calculated was 50 for the sample population, and 50 for the experimental group.

The two groups of preterm infant-mothers were recruited from those who were admitted to the NICU. The first set of samples ( n=50) was recruited from early February 2018 until July 2018. The preterm infant-mother dyads who were admitted within these months were allocated to the control group, while recruitment for the experimental group of preterm infant-mother dyads (n=48) was initiated from early September 2018 until April 2019, after completion of the intervention program for the nurses. In both groups, the sample size for the control group was (n=48) and the experimental group (n=48), for a total sample size of (n=96).

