### **3.19.1 Analysis of Quantitative Data**

Graduate Package 23.0 of the Statistical Package for Social Sciences (SPSS) provided tools to analyze the data required to achieve the research objectives:

In the pretest of dependent variables, data from the mothers and infants were evaluated for homogeneity, normality, variability, and data normality in the pretest. Nevertheless, the variance test for the nurses' data was not homogeneous since we were dealing with the same group, the data were normally distributed and the variances between the groups were equal, and the sample size was acceptable (no less than 30 cases per group). The number and proportion were stated as continuous variables and categorical variables. Continuous variables were compared for normally distributed variables ('mothers' and 'infants') using the independent t-test and variance analysis (ANOVA/ANCOVA). Pearson's chi-square test was used because the independent variables were nominal categorical variables. The Chi-square test was applied with normally distributed data to establish associations between independent variables, such as age, years of service as RN, years of working in NICU and educational qualification level, and dependent variables: perception, knowledge and outcomes improvement: weight gain, length of hospitalization stay and breastfeeding rates. In addition, the Shapiro-Wilk test was used to test data normality for both the pre and post-test, as the sample was below 50 per arm. To assess the effect of the structured kangaroo care educational program (KC-EP) on mothers', infants' and nurses' outcomes, for the data on mothers, infants and nurses, the general linear model (GLM) univariate analysis of variance and covariance analysis was used. GLM and repeated measures were used to analyze the main effects and interaction effects of KC outcome variables, and to examine the hypotheses of the outcomes.

Table 3.4: Summary of Statistical Analysis of Quantitative Data Plan

No.	Objectives	Measurement Variables	Statistical analysis

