categorical variables are both independent and dependent variables. Therefore, covariance analysis was used to correct the observed effects on the outcome variables of potential confounders. The summary of the statistical analysis used for all research questions is outlined in Table 3.14. Each of the statistical tests is two-tailed. A p-value below 0.05 was assumed to show statistical significance.

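### Repeated-measures GLM for the mothers' T0, T1 and T2 scores keeps only mothers with all three visits, although the plan expects missing data; a mixed model in the same package would use the partial follow-up

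*Combined protocol and SAP*

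**What the plan says.** Section 3.16.3 has the mothers complete the same questionnaire at T0, T1 and T2. For the analysis, section 3.19.1 names SPSS 23.0 and states that "GLM and repeated measures were used to analyze the main effects and interaction effects of KC outcome variables". In Table 3.4 the row for the mothers' perception, knowledge, perceived barriers and stress lists repeated measures alongside chi-square and GLM. The weight-gain row lists chi-square, GLM and t-test, without repeated measures.

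On sample size, section 3.7.2 says: "The sample size for mother-infant dyads was calculated using the two-sample independent t-test". The outcome sized is weight gain. The result, 35 per group, becomes "Additional 30% = 50 subjects for each group", and the reason given is "to account for possible missing values and non- responses". The same section reports 50 controls recruited but a final size of 48 per group, 96 in all.

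No section says what happens to a mother who misses T1 or T2.

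**The concern.** A repeated-measures GLM takes one row per subject and needs every visit in that row. This is a general property of the procedure; the documents do not state it. A mother with T0 and T1 but no T2 is removed entirely, including her T1 score. The plan therefore expects missing data and names a method that throws away part of what is observed.

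Enlarging the sample replaces lost numbers, but it does not remove bias. Three features of the plan make it plausible that completion is related to the outcomes or differs by arm:

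- T1 and T2 forms are collected at clinic return, with email for mothers who could not keep to the time (section 3.16.1). A stressed mother, or one whose infant is doing poorly, may be less or more likely to respond.
- Tables 3.2(a) and 3.2(b) schedule the WhatsApp messages and telephone follow-ups for the experimental group only.
- Section 3.16.4 excludes experimental-group infants who no longer meet study requirements, and section 3.18 disqualifies experimental-group mothers who discuss the study with other participants.

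If mothers with three complete visits differ from the rest, and differ in different ways by arm, the group-by-time comparison of scores is distorted.

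**Working it through.** **1. Reproduce the plan's sample size.** Inputs from section 3.7.2: difference 0.54, SD 0.8, Z values 1.96 and 0.842. Section 3.19.1 sets two-sided testing at 0.05.

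n = 2 × (1.96 + 0.842)² × 0.8² / 0.54² = 34.46, or 34.65 with the plan's rounding of 0.54² to 0.29. Both round up to 35.

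**2. Reproduce the allowance.** 35 / (1 − 0.30) = 50, as stated. Multiplying instead gives 35 × 1.30 = 45.5, or 46. The plan therefore used the division, which provides for 30% of dyads contributing nothing. That is what complete-case deletion does to them: 50 × 0.70 = 35.0.

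**3. Apply the same loss to 48 per arm.** 48 × 0.70 = 33.6. Power at a standardised difference of 0.54/0.8 = 0.675:

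| n per arm | Exact two-sided t-test | Normal approximation |
|---|---|---|
| 33 | 77.1% | 78.3% |
| 34 | 78.3% | 79.5% |
| 35 | 79.5% | 80.6% |
| 48 | 90.5% | 91.1% |

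Against 35, the exact loss is 79.5 − 78.3 = 1.2 points at 34 and 79.5 − 77.1 = 2.4 points at 33. An arm of 48 drops below 35 complete dyads once more than 1 − 35/48 = 27.1% are incomplete; an arm of 50 does so above 30.0%. The difference between those two thresholds comes from the two dyads per arm, not from the analysis method.

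**4. What the method discards.** The documents give no rate by visit, so this step is illustrative. Assume 48 mothers per arm, T0 complete, and 15% missing at each of T1 and T2. If the losses are independent:

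- all three visits: 48 × 0.85² = 34.7
- exactly one follow-up visit: 48 × 2 × 0.15 × 0.85 = 12.2
- no follow-up visit: 48 × 0.15² = 1.1

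Repeated-measures GLM uses the 34.7. A mixed model on T1 and T2 uses 34.7 + 12.2 = 46.9. The gain depends on overlap. If the same mothers miss both visits, nobody has partial follow-up and the two methods use the same 48 × 0.85 = 40.8 mothers. If no mother misses both, 48 × 0.30 = 14.4 mothers have one visit each and all are discarded. The number discarded at this rate therefore lies between 0 and 14.4 per arm.

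**5. Bias.** Restricting to mothers with three visits is in general biased when missing a visit depends on earlier observed scores. A likelihood-based mixed model remains valid in that case, provided missingness depends only on data in the model. Neither method handles missingness that depends on the unobserved score itself.

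**The case against.** The strongest counter-argument is that the plan has already paid for missing data. It has, as far as numbers go. A reader might infer that the evaluable sample must fall below the required 35. The documents do not support that, because the 30% was built in as 35/(1 − 0.30). Nor does it help to set 77–78% power against 90.5% at 48: that compares a 30% loss with no loss, whereas the design target of 35 itself gives 79.5% by the exact test.

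A reader might also take the 30% as a rate at each visit, leaving 48 × 0.70² = 23.5 and about 64% power. Section 3.7.2 applies the 30% once, to group size, and gives no rate per visit.

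The requirement of 35 belongs to a t-test on weight gain, and Table 3.4 does not list repeated measures in that row. The mothers' scores have no sample-size requirement to fall short of. The general sentence in section 3.19.1 could extend repeated measures to serial weights, but the more specific table does not.

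Whether 48 is before or after losses is unclear. The control figures (50 recruited, 48 final) suggest it is net of losses. Sections 3.16.2 and 3.16.4 describe 48 experimental dyads at consent and assignment, which reads as an enrolment count.

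It can also be said that the plan states no missing-data method, that Table 3.4 lists GLM as well as repeated measures, and that a univariate GLM at a single visit would not delete a mother for missing another. All of this is true. But time and interaction effects across three visits are what repeated measures is listed for, and no alternative handling is offered. No dropout pattern is reported either, so bias is a plausible risk and not a demonstrated one.

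**Conclusion.** The point stands for the mothers' perception, knowledge, barrier and stress scores. The named procedure keeps only mothers with T0, T1 and T2, discards usable follow-up from the others, and is open to bias if missingness depends on earlier scores. The amount discarded cannot be fixed from the documents; under the assumed 15% per visit it is 0 to 14.4 mothers per arm, and 12.2 if losses are independent.

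No shortfall below 35 should be claimed. If 48 per arm is counted before losses and a full 30% is then lost, 33 to 34 remain, about 1 to 2.5 points of power below the level at 35. That follows from enrolling 48 rather than 50.

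The conclusion rests on two things outside the text: the complete-case behaviour of the procedure, and the possibility that follow-up response is related to observed scores. The change is worth making because it improves on the stated method at almost no cost.

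**What to change.** In section 3.19.1 and the first row of Table 3.4, replace repeated-measures GLM for the mothers' scores with a linear mixed model (MIXED in the same package). Use T1 and T2 scores as outcomes, with group, time and group-by-time as fixed effects, the T0 score as covariate and an unstructured covariance. With two follow-up visits that covariance has only three parameters. Any confounders already planned for covariance analysis can enter in the same way. Include every mother with a T0 score and at least one of T1 and T2. Use the same model for serial weights if repeated measures is intended for them.

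Report the number of mothers with data, and the reasons for absence, by arm and visit. List separately the losses from the experimental-group-only exclusions in sections 3.16.4 and 3.18. The mixed model does not repair those, because dyads removed by rule in one arm only are not missing data of the kind it can handle.

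The cost is analysis syntax and one extra table. Data, software and sample size are unchanged.

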The control group mothers came for visits and saw their preterm infants once a day for 30 minutes to 1 hour, and exercised KC if they were interested. This was the NICU's routine practice. The control group of mothers continued routine ward practice and standard hospital care. Mothers who declined to participate during the time of the study were excluded. For participation in the study, a small token gift was given to (n=48) mother-infant dyads at the control group.

Upon their premature infant's discharge from the hospital, the mothers were reminded to answer the same standardized questionnaire (QI) for T0, T1, and T2. The following posttest questionnaires (Questionnaire I: enclosed in the envelope) were given to the mothers at the NICU or the Pediatrics Clinic on the 1st and 3rd month, when they came for their premature infant's follow-up, and were returned the same day. Consequently, some of the data were collected and sent by email if the mothers could not keep to the time (received on the same day).

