After the preterm infants were allocated to the control group or experimental group, they were observed daily, and all observations related to the outcomes of the study were documented in the KCPR booklet i.e. velocity of weight, temperature before, during and after, mode of feeding, type of milk taken and duration of KC provided (in hours/day/week), date of admission and date of discharge in days. In the study by Biswas, Malpani & Ekka, (2016) temperature measurement was taken 10 minutes after KC. However, in this study the

temperature measurement was taken 10 minutes before, 20 to 30 minutes during KC and 10 minutes after the implementation of KC and a regular clinical examination was given in a minimal period of time to avoid hypothermia and cold stress. In the experimental group, duration of KC (in an hour/day) was measured from an accumulated daily 1 hour per day, 4 to 5 hours a week. However, according to Ludington-Hoe, Susan, Morgan, K. & Abouelfetoh (2008), KC is best provided 1 hour a day and 7 days a week until discharge. KC was continued until the premature infant was 3 months old, according to the study requirements. If any problems were detected during KC, they were either rectified or the preterm infant was disqualified from the study. Premature infants were discharged when they showed a good sucking reflex with breast or bottle feeding and had been gaining weight of more than 15g/day to 20g/day for at least three successive days and had achieved a predetermined weight of 1.7kg, in accordance with hospital protocol. On discharge, the nurses routinely advised mothers to come for follow-up until their infant had reached a weight of 2500 grams and to continue breastfeeding. For primary and secondary outcomes, the data from both groups were collected at T0, T1, and T2. The premature infants were followed-up until they were discharged. Conversations and communication between mothers and researchers continued through telephone calls or Whatsapp chat groups accordingly. All related information on KC was shared through the WhatsApp chat group among mothers in the experimental group so that they would remain KC compliant and continue KC at home.

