### **3.17 Method of Data Collection for Nurses**

The nurses were screened and recruited based on universal sampling. Method of data collection for nurses was similar to that for mothers, whereby, prior to the KC-EP for nurses, pretest data on nurses' perception, knowledge, and practice were collected using the KCQ tool in Questionnaire II. The data for nurses were collected within a 2 month period from 1st August 2018 to 30th September 2018 for the pretest-posttest groups of nurses. The researchers briefed the nurses and encouraged them to take part in the study by presenting verbally brief information to the head nurse in charge of the unit, with two forms of consent given to the nurses on the same day as the pretest program. All nurses who attended were recorded with their name, identification code number, date of attendance and signature in order to plan the date for their following posttest. To ensure confidentiality and privacy, each returning questionnaire was assigned an identification code number. The consent form together with the questionnaire was stamped, starting with nurse 01(N01), with the code number in the top right corner. If the nurses refused to continue with the study, they were instructed to notify the researcher and ask for a withdrawal. Upon receiving an application for withdrawal from the study, the researcher found and destroyed the questionnaire, which was submitted based on the code number. The pretest (Questionnaire II) was given to all nurses before the KC-EP was administered to them. The nurses were instructed to complete Questionnaire II, which took approximately 15 to 20 minutes to complete, without reference to any resources before the KC-EP session for nurses was conducted. Nurses were asked to return the questionnaires upon completion, with one copy of the informed consent. All nurses were advised to keep one copy of the informed consent for their records. Following the completion of the KC-EP, the nurses were told of the posttest sit after the 7th day of the pre-test and intervention program. The same structured Questionnaire II was administered to the nurses at the posttest. Data collection among nurses was conducted within the stipulated time.

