### **3.17.1 Nursing Outcome Variables**

The data for nursing outcomes were collected in Phase II, historical control data were collected through a retrospective nurse audit of knowledge and skills in relation to KC management practices and assessing data on KC implementation techniques among mothers with premature infants. The nurses' perception, knowledge, and practice in relation to KC implementation were assessed using a set of structured questions, Questionnaire I for nurses, via a pre-test and then reassessed in a 7th day post-test following the program.

The researcher briefed the nurses and invited them, through a verbal briefing to the head nurse in charge of the selected unit, to participate in the study. On the same day as the pre-test, the Questionnaire I was given to the nurses, with two consent forms. Name, identification code number and date of attendance of the nurses who attended were recorded in order to plan the follow-up date for the post-test. The returned questionnaire was given an identification code number to ensure confidentiality and privacy. The consent form, including the questionnaire, was stamped in the right top corner with the code number, starting with nurse 01(N01). When nurses declined to continue the study, they were told to contact the researcher to ask for a withdrawal. Upon receiving an application for withdrawal from the study, the researcher destroyed the questionnaire, which was submitted based on the code number. All nurses were instructed to sit for the post-test on the 7th day after the pretest. The nurses were instructed to complete Questionnaire I for the pretest, which took about 15 to 20 minutes to complete, without referring to any resources before the KC-EP for nurses was conducted. Nurses were asked to return the questionnaires upon completion, together with one copy of the informed consent document. All nurses were expected to keep one copy of the informed consent form in their records. On the 7th day, the nurses were told to answer the same set of questions that had been used in the pretest. It was anticipated that an interval of 7 days would enable the posttest group nurses to translate their theoretical expertise into action and gain experience in evaluating, managing, and promoting the implementation of KC and also breastfeeding for mother-infant dyads through hands-on practice in the NICU environment.

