Firstly, the researcher collected a group of participants from the infant-mother dyads for the control group and made them comfortable. An orientation to the study was given before administering Questionnaire II, which required approximately 10 to 15 minutes to complete. All mothers were instructed not to interact or communicate while answering the questionnaire. On the same day, participants were asked to return the completed questionnaires to the researcher. An identification code number was provided for each

[figure not shown]
returned questionnaire to ensure confidentiality and privacy. The consent form and the questionnaire were stamped at the top right corner with the code number, for each set of questionnaires ( $T_0$ ,  $T_1$  and  $T_2$ ), starting with control group 01 (CG01) for the control group of mother-infant dyads. The pretest and posttest used the same structured Questionnaire II for baseline data from the mother-infant dyads in the control group. However, this group did not receive any special education program or any input related to KC from the researcher. All mothers were informed to answer the post-test questionnaire within the stipulated time of 1 month and 3 months after the discharge of their infant from the NICU. The collection of data from the control group of mothers was completed within six months, starting from early February 2018 to the end of July 2018.

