Finally, the researcher recruited a group of mothers with premature infants for the experimental group, returning to them in 48 hours. The researcher orientated the mothers to the nature of the study and administered Questionnaire I for the pretest, which required 10 to 15 minutes to complete. All mothers were instructed to not share or discuss anything with other group members and if discussion took place they were disqualified to continue the study. Once the questionnaires were completed they were collected by the researcher; the mothers required 10 to 15 minutes to complete Questionnaire I. The infant-mother participants' baseline data were gathered regarding demographic characteristics and KCQs tool (perception, knowledge, perceived barrier and stress level) for the pretest on KC technique. After the pretest, the mothers in the experimental group obtained information on KC in a group of two to four participants via the face to face teaching method; each group was accompanied by two of the nurses who were available in the NICU at that period of time. The KC-EP for mothers was conducted by the researcher and included a theory and practical session. The mothers were requested to answer the posttest at the 1st month and 3rd month of their premature infant's life after their discharge from the hospital. The same Questionnaire I was provided to the mothers for the posttest data. The collection of data from the mothers

was carried out within the stipulated time. After the data gathering process, the researchers thanked all the study participants as well as the authorities for their cooperation.

[figure not shown]

Figure 3.3: Flow Chart for Data Collection

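### Control counts disagree (50 recruited, 48 in the sample), and stated rules destroy withdrawing nurses' questionnaires and disqualify mothers in one arm only

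*Combined protocol and SAP*

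**What the plan says.** **Controls.** Section 3.7.2 states "The first set of samples ( n=50) was recruited from early February 2018 until July 2018" and allocates those dyads to control. The same paragraph ends: "In both groups, the sample size for the control group was (n=48) and the experimental group (n=48), for a total sample size of (n=96". Section 3.16.1 (token gift) and Section 3.16.4 (infants on routine care) also give 48 controls. Section 3.16.1 adds: "Mothers who declined to participate during the time of the study were excluded".

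**Nurses.** Under Section 3.17, when a nurse applies to withdraw, "the researcher found and destroyed the questionnaire". Section 3.17.1 repeats it: "the researcher destroyed the questionnaire, which was submitted based on the code number". Both sections also record each attending nurse's name, code number and attendance date.

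**Mothers and discussion.** In Section 3.18, experimental mothers are told not to share or discuss with other group members, and "if discussion took place they were disqualified to continue the study". Control mothers, in the same section, are "instructed not to interact or communicate while answering the" questionnaire, and no consequence is given.

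**Analysis.** Section 3.19.1 names the tests. It does not define an analysis set or say how withdrawn or disqualified participants are handled.

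**The concern.** This is a non-randomised comparison of groups recruited one after the other, so the two arms need to be enrolled, followed and counted under the same rules. People who withdraw or are removed after enrolment may differ from those who stay in ways that bear on the outcomes.

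Three things make that hard to check here. The control figures differ by two, with no reason in the text. A withdrawing nurse's pretest is lost, so her baseline cannot be compared with that of nurses who stayed. A removal rule is written for experimental mothers only. At stake is whether a reader can tell that the results cover everyone enrolled.

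**Working it through.** **Inputs.** From Section 3.7.2: z-values 1.96 and 0.842, difference 0.54, SD 0.8, a 30% allowance, 50 controls recruited, 48 in the sample. From Section 3.7.3: 47 nurses invited. The text of Section 3.7.2 also cites a mean difference of 8.41 that does not enter the formula. Every comparison below with the planned effect uses 0.54.

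**1. The plan's own figure.** n = 2 × (1.96 + 0.842)² × 0.8² / 0.54² = 34.46, which rounds up to 35 per group (34.65 with the document's rounded 0.29). Allowing for 30% loss, 35 / 0.70 = 50. Both figures reproduce. So 50 is also the planned size per group, which matters when judging whether the 50 recruited is a real count.

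**2. The gap.** 50 − 48 = 2, and 2/50 = 4.0%, far inside the 30% allowance.

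**3. Power.** Normal approximation, difference 0.54, SD 0.8: 91.1% with 48 per group and 92.1% with 50. Power is not the issue.

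**4. Possible bias from two controls.** The documents give no data on them. Assume both differ from the other 48 by k SD in the same direction. The mean of all 50 then differs from the mean of the 48 by 2k/50 = 0.04k SD. As a share of the planned difference, this is 0.04k × 0.8 / 0.54.

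| k (assumed) | Shift in control mean | Share of 0.54 |
|---|---|---|
| 1 | 0.04 SD | 6% |
| 2 | 0.08 SD | 12% |
| 3 | 0.12 SD | 18% |

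**5. Weight of one removal.** One nurse is 1/47 = 2.1% of the pre-post sample. One experimental mother is 1/48 = 2.1% of her arm. No number of removals is reported, so no bias can be calculated for either group.

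**6. The no-conferring rules side by side.** Both sit in Section 3.18. Controls are told not to interact while completing the questionnaire, and nurses are told not to interact with each other. Neither faces a stated penalty. For experimental mothers the sentence falls between handing out the pretest and collecting it, and carries disqualification. The purpose looks the same in all three groups; only one has a removal rule.

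**The case against.** The strongest reply is that much of what a reader might infer is not in the text. Most of that reply stands.

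- **Two controls withdrew and their data were discarded.** Nothing says so. Destruction is written only for nurses, and what happens to a mother's existing data is not stated. Since 48 appears elsewhere and 50 is the planned figure, the recruited 50 may be a slip. Figures 3.2 and 3.3, the data-collection flow charts, are not reproduced in the copy reviewed and could show participant flow.
- **Section 3.16.1 drops control mothers after enrolment.** The verb declined more naturally means refusal to join. Section 3.16.4 has a parallel rule, in a consent context, for mothers who refused.
- **Controls were dropped with their outcomes known.** Section 3.16 says control data were recorded and then analysed, but gives no analysis date.
- **The number of nurses who left is lost.** The attendance record in Sections 3.17 and 3.17.1 keeps it. Only the answers go, and only when the nurse applies to withdraw. Sections 3.17 and 3.18 refer to all 47 nurses.
- **Taking part in the intervention disqualifies a mother.** Mothers were taught in small groups, and "All related information on KC was shared through the WhatsApp chat group among mothers in the experimental group", so a literal reading would catch ordinary participation. The sentence's place within the pretest procedure does not support that reading.

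Three things survive the reply: the unreconciled count, the destruction rule as written, and a penalty stated for one arm only.

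**Conclusion.** The point holds as a matter of stated rules and an unreconciled count. It is not evidence that participants were in fact lost. If followed, the nurse rule deletes usable pretest answers, and leavers then cannot be compared with stayers. The discussion rule, if followed, removes dyads after enrolment in the experimental arm alone. The control count is either unreported loss or an error, and the text cannot settle which.

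The size of any bias is unknown for nurses and experimental mothers. For the controls it is small: 4% of those recruited, and 0.04 to 0.12 SD under the assumption that both differ from the rest by 1 to 3 SD in the same direction. The effect on power is about one percentage point. The case for changing the plan is that the change is cheap and makes the results checkable.

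**What to change.** 1. **Control count.** Reconcile 50 with 48 in Sections 3.7.2, 3.16.1 and 3.16.4. If 50 were enrolled, analyse all 50 for discharge weight and length of stay from the hospital record, and for questionnaires up to the point each mother stopped, subject to consent. Report the reasons for loss. If 50 is an error, correct it.
2. **Section 3.16.1.** Say whether the exclusion of mothers who declined applies before or after enrolment.
3. **Nurses (Sections 3.17 and 3.17.1).** On withdrawal, collect nothing further, keep completed questionnaires unless the nurse asks for deletion, and log the date and stage of withdrawal. If any questionnaires have already been destroyed, report how many, using the attendance record.
4. **Discussion rule (Section 3.18).** Replace the disqualification with the instruction given to controls, use it in both arms, log breaches as deviations, and keep the dyad in the analysis. State whether anyone was disqualified.

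The cost is protocol and consent-form wording, plus a check of enrolment records. The small downside is that keeping data after withdrawal must be stated in the consent form, with deletion on request. The consent forms were not in the copy reviewed, so what participants have already been told needs checking first.
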